9.5.4.2 VLU Arm

100% re-epithelialization will be assessed every week (except during virtual visits) for 16 weeks for VLU patients or until 100% re-epithelialization, whichever occurs first. Persistence of wound closure will be verified via confirmatory visit within 2 weeks after complete closure has been first determined.

For the primary endpoint of 100% re-epithelialization at week 16 a Farrington & Manning test will be used. Noninferiority for synthetic hybrid-scale fiber matrix will be demonstrated if the lower bound of the 90% CI of the difference in proportions lies above the non-inferiority margin of -10%.

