5.7 Randomization

The randomization process will be pre-programmed into the electronic data capture (EDC system) prior to enrollment of the first study patient.

Once the patient meets all enrollment criteria and has completed the 2-week run-in period, the patient will be randomized. Patients with a DFU(s) will be randomized to receive either synthetic hybrid-scale fiber matrix (treatment group) or SOC (control group). Patients with a VLU(s) will be randomized to receive either synthetic hybrid-scale fiber matrix (treatment group) or living cellular skin substitute (control group).

Randomization will be stratified by wound size:

- DFUs will fall into two groups ($>1.0 \text{ cm}^2$ and $< 12.5 \text{ cm}^2$) and ($\geq 12.5 \text{ cm}^2$ and $< 25 \text{ cm}^2$). Patients within each group will be randomized in a 1:1 ratio to receive either synthetic hybrid-scale fiber matrix or SOC.
- VLUs will fall into two groups: ($>1.0 \text{ cm}^2$ and $< 25 \text{ cm}^2$) and ($\geq 25 \text{ cm}^2$ and $< 50 \text{ cm}^2$). Patients within each group will be randomized in a 1:1 ratio to receive either synthetic hybrid-scale fiber matrix or living cellular skin substitute.

Once the patient is ready to be randomized, the randomization form will be completed by study personnel in the electronic data capture (EDC) system. The randomization assignment will be obtained from the EDC system prior to the initial application of the study product. If a patient has more than one wound that meets all enrollment criteria, then all wounds will be randomized to the same study product. The largest wound that meets enrollment criteria will determine the size stratification for the patient.

Any patients that exit the study before randomization are considered screen failures. A study exit CRF shall be completed if the patient is not eligible for randomization.

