9.3.2 VLU Arm

Sample size calculations were performed using a Farrington & Manning test for non-inferiority of the synthetic hybrid-scale fiber matrix group compared to the control group. Under assumptions of a closure rate of 75% for the synthetic hybrid-scale fiber matrix group, 50% for the control group, and a noninferiority margin of 10%, this results in a sample size of 24 per group (48 total) that provides a power of 0.8 and one-sided alpha of 0.05. After allowing for an assumed 20% lost to follow up, this results in a total sample size of 60 patients.

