9.5.4.1 DFU Arm

100% re-epithelialization will be assessed every week (except during virtual visits) for 12 weeks for DFU patients or until 100% re-epithelialization, whichever occurs first. Persistence of wound closure will be verified via confirmatory visit within 2 weeks after complete closure has been first determined.

For the primary endpoint of 100% re-epithelialization at week 12 a two-stage analysis will test first if the rate of 100% re-epithelialization is non-inferior between groups using a Farrington & Manning test. Noninferiority for synthetic hybrid-scale fiber matrix will be demonstrated if the lower bound of the 90% CI of the difference in proportions lies above the non-inferiority margin of -10%.

If non-inferiority is shown, superiority of synthetic hybrid-scale fiber matrix over Standard of Care will be tested using a chi-square test.

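### The VLU arm is planned on a 25-point advantage but pre-specifies only non-inferiority, so a superiority finding there would be post hoc; a nested superiority step would cost nothing

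*Combined protocol and SAP*

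**What the plan says.** All references are to the combined protocol and SAP.

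- **Planning (9.3.2).** The VLU arm assumes a "closure rate of 75% for the synthetic hybrid-scale fiber matrix group, 50% for the control group", with a 10-point margin: "this results in a sample size of 24 per group (48 total) that provides a power of 0.8 and one-sided alpha of 0.05". Enrolment follows: "After allowing for an assumed 20% lost to follow up, this results in a total sample size of 60 patients".
- **VLU hypotheses (9.1.1.2).** One pair only: a difference at or below -0.10 against a difference above it.
- **VLU analysis (9.5.4.2).** "For the primary endpoint of 100% re-epithelialization at week 16 a Farrington & Manning test will be used". Success means that the lower bound of the 90% confidence interval lies above -10%. No further step follows.
- **DFU analysis (9.5.4.1).** The same first stage, then: "If non-inferiority is shown, superiority of synthetic hybrid-scale fiber matrix over Standard of Care will be tested using a chi-square test". No level or sidedness is given for this chi-square test.
- **Missing data (9.6).** On the imputed datasets the DFU arm uses the one-sided Farrington & Manning test. The VLU arm uses a one-sided Fisher's exact test, and no margin is mentioned.
- **Population (9.2).** The mITT population is primary for efficacy.

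**The concern.** The arm with the larger planned advantage has no superiority step, and the arm with the smaller one does. The documents give no reason for the difference. Section 2.2 says that the results are meant to inform payor coverage decisions. If the planning rates are right, the only pre-specified VLU conclusion is that the matrix is not worse by 10 points or more. A superiority statement would then be open to the charge that it was chosen after the data were seen.

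Timing matters. The VLU interim is unblinded, and section 9.4 sends its results to a select group at the sponsor. A superiority step added after that point would look data-driven.

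**Working it through.** **1. Reproduce the plan's figure.** Inputs from 9.3.2 and 5.7: rates 0.75 and 0.50, margin 0.10, one-sided alpha 0.05, power 0.80, 1:1 allocation.

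n per group = [z(0.95)·s0 + z(0.80)·s1]² / (0.25 + 0.10)²

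- s0 uses the rates restricted to a difference of -0.10, which are 0.566 and 0.666: s0 = √(0.566×0.434 + 0.666×0.334) = 0.684.
- s1 = √(0.75×0.25 + 0.50×0.50) = 0.661.
- n = [(1.645×0.684 + 0.842×0.661) / 0.35]² = 23.09, so 24 per group. Then 48/0.8 = 60 enrolled.

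The stated 24 and 60 reproduce.

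**2. Power of a superiority test at the same rates.** With pooled rate 0.625, the normal approximation at one-sided 0.025 is

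Φ{[0.25√n − 1.960·√(2×0.625×0.375)] / 0.661}

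This gives Φ(−0.177) = 43% at n = 24 and Φ(0.041) = 52% at n = 30. Summing binomial probabilities over all outcomes of the uncorrected chi-square test gives the exact values:

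| Arm | Planned rates | Per group | Exact power, one-sided 0.025 |
|---|---|---|---|
| VLU | 75% v 50% | 24 (48 evaluable) | 45% |
| VLU | 75% v 50% | 30 (all 60 evaluable) | 52% |
| DFU | 75% v 60% | 44 (88 evaluable) | 34% |
| DFU | 75% v 60% | 55 (all 110 evaluable) | 40% |

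For 80% superiority power in the VLU arm, n = [(1.960×0.685 + 0.842×0.661)/0.25]² = 57.7. That is 58 per group, or 116/0.8 = 145 enrolled, above the cap of 90.

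**3. An example.** Suppose the VLU arm observes exactly its planning rates, 18/24 against 12/24.

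- Non-inferiority: z = 0.35/(0.684/√24) = 2.51, above 1.645, so it is met.
- Superiority: z = 0.25/√(0.625×0.375×2/24) = 1.79. This passes one-sided 0.05 (1.645) but not one-sided 0.025 (1.960).

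The claim therefore depends on a level that the plan does not state for either arm.

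**4. Alpha.** With a zero margin the Farrington & Manning statistic is the pooled z, whose square is the chi-square statistic. Superiority on the same endpoint and population, at the same or a stricter level, is therefore nested in non-inferiority. In exact enumeration at 24, 30, 36 and 45 per group, the probability of superiority without non-inferiority, both at one-sided 0.05, was zero to four decimals.

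Type I error of the chi-square test at one-sided 0.025, for equal rates of 0.50, 0.60 and 0.75:

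- 24 per group, fixed: 3.0%, 2.8%, 2.6%.
- 30 per group, fixed: 2.6%, 2.4%, 2.5%.
- 30 per group with the VLU re-estimation rule (simulated, 15 per group at the interim, no loss): 2.6%, 2.5%, 2.6%.

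The small excess at 24 per group comes from the large-sample test, not from the sequence. Re-estimation adds about 0.1 point.

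**The case against.** **Non-inferiority is the stated design.** The trial is labelled non-inferiority, and the VLU hypotheses, sample size, re-estimation and primary analysis all agree with that. No stated VLU objective goes untested and no stated figure is wrong. This stands: the point is an improvement, not a correction of the primary test.

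**The arms may differ on purpose.** Non-inferiority to standard of care says little, whereas non-inferiority to an approved active product is a usable result. The log in section 15 lists 9.5.4.1, but not 9.5.4.2, among the sections revised when standard of care became the DFU comparator. That may explain the asymmetry, but the plan does not say so, and it gives no reason to forgo a free second step.

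**A reader might infer that VLU superiority could never be shown.** The documents do not support that. A 90% interval above zero, if built consistently with the test, shows superiority at one-sided 0.05. Only pre-specification is missing.

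**A reader might take the Fisher's exact test in 9.6 as a VLU superiority test.** Without a margin it would ordinarily test zero difference. But 9.6 presents it as the counterpart of the DFU non-inferiority test on imputed data, with no superiority hypothesis, level or place in a sequence. It is an inconsistency with 9.1.1.2 and 9.5.4.2, not a pre-specified claim.

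**The gain is moderate.** This stands: even if the planning rates hold, superiority at one-sided 0.025 would be missed about half the time.

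**Conclusion.** The concern holds as a missed opportunity of modest size. The VLU arm has about a 45% to 52% chance of showing superiority at one-sided 0.025, against 34% to 40% in the DFU arm, where the step is pre-specified. These figures rest on the plan's own closure rates, 1:1 allocation, an uncorrected chi-square test, and between 20% loss and none.

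A reader might quote the exact power of 70% at 45 per group, the 90-patient cap. That treats the cap as a fixed design. Section 9.4.2 allows an increase only when interim conditional power is at least 0.43 and below 0.80. In simulation at the planned rates (15 per group at the interim, no loss) the arm reaches 45 per group in about 9% of trials. Superiority power in those trials is about 56%, and about 55% over all trials. The 70% figure should not be used.

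Nothing here weakens the non-inferiority test or its sample size.

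**What to change.** Before the unblinded VLU interim:

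1. Add to 9.1.1.2 and 9.5.4.2: *Once non-inferiority is met, test superiority over the living cellular skin substitute in the mITT population with a chi-square test at one-sided 0.025 (two-sided 0.05).* If superiority is not intended, say so instead.
2. In 9.5.4.1, state the level and sidedness of the DFU chi-square test.
3. In 9.6, replace the VLU one-sided Fisher's exact test with the Farrington & Manning non-inferiority test, so that it agrees with 9.1.1.2 and 9.5.4.2.

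The cost is a few sentences in four sections. Enrolment stays at 60, no data are added, and the one-sided 0.05 for non-inferiority is unchanged.

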9.5.5 Secondary Endpoints

The following secondary endpoints will be summarized for exploratory purposes. There are no plans for statistical testing of secondary endpoints.

Decrease in Wound Area from Baseline

The difference in wound area from baseline to each time point will be summarized for each treatment group in each arm. The difference in mean percent change in size between the treatment group and control group will be calculated for each timepoint. Wound area measurements will be made via the eKARE inSight system every week (except during virtual visits) for 12 weeks for DFU patients and 16 weeks for VLU patients (except during virtual visits), or until 100% re-epithelialization, whichever occurs first.

Time to Wound Closure

The time to wound closure will be summarized by proportion of patients with wound closure at each timepoint for each treatment group in each arm. The difference in proportion of patients with wound closure between the treatment group and control group will be calculated for each timepoint. Persistence of wound closure will be verified via confirmatory visit within 2 weeks after complete closure has been first determined.

Number of Product Applications

The number of product applications will be summarized for each treatment group in each arm. The difference in mean number of applications between the treatment group and control group will be calculated for each timepoint. Product applications will be defined as the number of product applications prior to complete wound closure within the treatment period for each study arm.

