5. STUDY CONDUCT

5.1 Schedule of Events for Diabetic Foot Ulcer (DFU) Patients:

Requirement	Run-In Period		Treatment Period (1) Week 0 is the initial application of study product and occurs 14 to 17 days after the start of the run-in period. Visit window for Weeks 1 through 12 is (± 3 days)												Two-Week In-Person Follow-Up (2)	Six-Month Telephone Follow-Up (2)	
	Start	7 days (± 3 days)	0	1	2	3	4	5 (3)	6	7	8	9 (3)	10	11	12	2 weeks after each wound closure (± 3 days)	Six-Months After Week 0 (± 1 month)
Informed consent	X																
Screening	X	X	X														
Demographics and history	X																
HbA1c	X(4)																
Vascularization (ABI, TBI or TcPO2)	X(4)																
Assessment of re-epithelialization				X	X	X	X	X	X	X	X	X	X	X	X	X (2)	
SF-36 Questionnaire and Pain Scale			X												X (5)		
Randomization			X														
Visual examination of wound(s) and imaging with eKARE inSight	X	X	X	X	X	X	X	X	X	X	X	X	X	X	X	X (2)	
Product application with Restrata			X		X		X		X		X		X		X		
Standard of Care			X	X	X	X	X	X	X	X	X	X	X	X	X		
Adverse events			X	X	X	X	X	X	X	X	X	X	X	X	X	X (2)	X (2)
Telephone follow-up																	X (2)

Notes:

- X – Requirement completed during patient encounter
- (1) – Treatment period visits will cease after 100% re-epithelialization of all study wounds is confirmed.
- (2) – An in-person visit two weeks (± 3 days) after 100% re-epithelialization is first identified, and a telephone call six months (± 1 month) after Week 0 are required for patients with 100% wound re-epithelialization of at least one wound. These visits are NOT required if there is not 100% re-epithelialization of any wound at or before 12 weeks.
- (3) – Weeks 5 and 9 may be conducted virtually at the discretion of the investigator and based on the evaluator’s assessment at Weeks 4 and 8. A visual wound assessment and wound imaging are not required if the visit is virtual. If the patient is randomized to SOC, then SOC would not be applied during a virtual visit (at the physician’s discretion).
- (4) – HbA1c and a vascularization assessment can be completed anytime within 60 days prior to Week 0
- (5) – SF-36 Questionnaire and Pain Scale will be completed during the visit when 100% re-epithelialization of all wounds is first identified or at 12 weeks (whichever occurs first)

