- Measurement and imaging of wound area via the eKare inSight platform according to the eKare inSight instructions. If debridement is completed during this visit, then the assessment must be completed after debridement.

5.10.4 Reapplication of the study product by personnel will occur:

- **DFU patients:**
 - **Randomized to Restrata: Biweekly up to 12 weeks**
 - **Randomized to Standard of Care: Weekly up to 12 weeks**
- **All VLU patients: Biweekly up to 16 weeks**

If 100% re-epithelialization is confirmed before 12 weeks for DFU patients or before 16 weeks for VLU patients, then re-application shall cease. For patients with more than one wound randomized to the study, re-application of product to each wound shall cease when 100% re-epithelialization of that wound is confirmed. The following will be completed by qualified personnel:

- Evaluate the amount of study product remaining in the wound.
- If the study product is completely intact (no resorption has occurred) and the wound is clean and clear of infection, then leave the product in place.
- The study product should be reapplied over previously absorbed material.
- If any of the study product material has resorbed, then evaluate for additional debridement prior to replacement with new study material.
- In the event the material does need to be removed from the wound bed prior to reapplication, use warm (37°C) sterile saline to continuously rinse the wound site to help detach the material, so as not to cause further damage to the wound bed. Forced removal may result in wound re-injury.

NOTE: If excess exudate collects under Synthetic hybrid-scale fiber matrix, the material should be thoroughly fenestrated to allow the exudate to drain.

5.11 3D Wound Measurement with the eKare inSight Platform

Wounds will be measured using the eKare inSight platform weekly from the beginning of the run-in period until 12 weeks for DFU patients or 16 weeks for VLU patients (except Weeks 5 and 9 if conducted virtually). If 100% re-epithelialization of all wounds is confirmed before 12 weeks for DFU patients or before 16 weeks for VLU patients, then

measurements shall cease. Qualified personnel who are trained on the system will be required to complete the assessment. **If debridement is completed at the visit, then the measurement must occur after debridement.**

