The inSight platform uses structured light to produce three-dimensional renderings of wounds and translates the data into area, length, width, depth and volume within seconds.

Each investigational site will be provided with one system, which will need to be returned to the Sponsor at study conclusion.

5.12 Virtual Visits at Weeks 5 and 9

Based on the evaluator's assessment of the wound image and at discretion of the investigator, Week 5 and Week 9 may be conducted virtually (via telephone call or web meeting) by un-blinded study personnel. A visual wound assessment and wound imaging via the eKARE inSight platform are not required if the visit is virtual. If a DFU patient was randomized to Standard of Care, then product reapplication is not required if the visit is virtual. The following will be completed during virtual visits:

- Collect information about adverse events and medications
- Collect information about wound drainage and dressing changes since the previous visit
- Discuss wound care recommendations including any needed dressing changes

At Week 4, the **evaluator** will complete an assessment of the wound image and determine whether or not 100% re-epithelialization is likely to occur before Week 5.

- If 100% re-epithelialization of any wound is likely to occur before Week 5 based on the blinded evaluator's assessment, then an in-person visit will be completed at Week 5.
- If 100% wound re-epithelialization is unlikely to occur before Week 5 based on the blinded evaluator's assessment, then the investigator will determine whether Week 5 will be completed virtually or in-person based on the patient's best interest. For DFU patients randomized to Standard of Care, a visit may be conducted virtually only if the investigator determines it is in the patient's best interest to forego product reapplication at Week 5.

At Week 8, the **evaluator** will complete an assessment of the wound image and determine whether or not 100% re-epithelialization is likely to occur before Week 9.

- If 100% re-epithelialization of any wound is likely to occur before Week 9 based on the evaluator's assessment, then an in-person visit will be completed at Week 9.

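### In the DFU arm, the planned Week 5 and Week 9 differences in wound area compare prognosis-selected patients, and the selection can differ between groups

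*Combined protocol and SAP*

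**What the plan says.** Section 9.5.5 plans a comparison of wound area at every visit week: "The difference in mean percent change in size between the treatment group and control group will be calculated for each timepoint". It notes that areas are not measured at virtual visits but does not take Weeks 5 and 9 out of the comparison. It also states: "There are no plans for statistical testing of secondary endpoints".

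Section 5.12 decides who is imaged at those weeks. At Week 4 the evaluator predicts from the image whether any wound will close before Week 5. If closure is "likely to occur before Week 5 based on the blinded evaluator's assessment, then an in-person visit will be completed at Week 5". If closure is judged unlikely, the investigator chooses between an in-person and a virtual visit, and "A visual wound assessment and wound imaging via the eKARE inSight platform are not required if the visit is virtual". The same steps apply at Week 8 for Week 9. Section 5.11 carries the exception into the measurement schedule ("except Weeks 5 and 9 if conducted virtually"), and note (3) to the DFU schedule in section 5.1 repeats it.

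One condition applies to a single randomized group: "For DFU patients randomized to Standard of Care, a visit may be conducted virtually only if the investigator determines" that forgoing that week's reapplication serves the patient. Matrix patients have no counterpart, because section 5.10 schedules matrix reapplication at even weeks only.

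Section 9.6 imputes missing closure status, a yes/no outcome. No section says how a missing wound area is handled.

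**The concern.** Whether an area exists at Week 5 or 9 depends on predicted healing and, in the DFU arm, can also depend on assignment. Patients expected to close are always measured, while slower healers may not be. If more slow healers are left out of one group's mean than the other's, the groups differ on paper even when healing is identical. Randomization does not protect against this, because the selection happens after it.

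At stake is a secondary result on healing. Section 2.2 lists decrease in wound size among the outcomes the study will provide and says payors need this information for coverage and reimbursement. Leaving out a test removes the p-value but does not remove bias from the reported difference.

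**Working it through.** **The plan's own figures.** The documents give no figure for the wound-area comparison. The DFU sample size in 9.3.1 (75% against 60%, margin 10 points, one-sided alpha 0.05, power 0.8) reproduces: the Farrington-Manning calculation gives 43.1, so 44 per group, with power 0.807 at 44, and 88/0.8 = 110. It is used below only as a group size.

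**Inputs from the documents.** Patients judged likely to close are always imaged. Those judged unlikely may not be (5.12). The extra condition binds DFU SOC patients only (5.12). Allocation is 1:1 (5.7).

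**Assumed inputs (none is in the documents).**
- pL: share judged likely to close, 0.1 to 0.3
- mL, mU: mean percent area reduction in likely and unlikely patients, 90 and 50 or 85 and 60
- q: share of unlikely patients still seen in person (qR for matrix, qS for SOC)

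Healing is set equal in the two groups, so any difference is spurious. Wounds already closed before the week in question are not modelled.

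**Formula.** Mean among imaged patients = [pL·mL + (1 − pL)·q·mU] / [pL + (1 − pL)·q].

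With pL = 0.2, mL = 90 and mU = 50 this is (18 + 40q)/(0.2 + 0.8q). With everyone imaged (q = 1) it is 58.0, the true mean. Three other values:
- q = 0.2: 26/0.36 = 72.2
- q = 0.5: 38/0.60 = 63.3
- q = 0.9: 54/0.92 = 58.7

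| qR / qS | Matrix mean | SOC mean | Spurious difference (points) | Range over all pL, mL, mU above |
|---|---|---|---|---|
| 1 / 1 | 58.0 | 58.0 | 0.0 | 0.0 |
| 0.5 / 0.5 | 63.3 | 63.3 | 0.0 | 0.0 |
| 0.8 / 0.9 | 59.5 | 58.7 | +0.8 | +0.3 to +1.1 |
| 0.5 / 0.8 | 63.3 | 59.5 | +3.8 | +1.5 to +4.5 |
| 0.3 / 0.8 | 68.2 | 59.5 | +8.7 | +3.7 to +9.6 |
| 0.2 / 0.9 | 72.2 | 58.7 | +13.5 | +6.2 to +14.4 |

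Plus means in favour of the matrix.

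**Cross-check by simulation.** The closure prediction was based on Week 4 status. Percent reduction was drawn with mean 60 and SD 30 and capped at 100, with a Week 4 to Week 5 correlation of 0.8 (all assumed). With 20% judged likely to close, the spurious differences were +3.5, +7.9 and +12.4 points for 0.5/0.8, 0.3/0.8 and 0.2/0.9. With the shares reversed (0.8/0.5) the difference was −3.5. With 44 per group and no true effect, the observed difference favoured the matrix in 84% of trials at 0.3/0.8 and 94% at 0.2/0.9, against 50% with full imaging.

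**VLU.** Section 5.12 sets no group-specific condition for VLU, and both groups are re-treated at even weeks (5.10). Equal use corresponds to the 0.5/0.5 row: both means are too high (63.3 against 58.0), but the difference is zero.

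**Proportion closed.** Section 9.5.5 also plans differences in proportion closed at each timepoint and does not say how virtual patients enter the denominator. If they count as not closed, the group with more virtual visits looks slightly worse, because a closure in that week is seen a week later. If they are dropped, that group looks better. The effect is not quantified. Any delay is probably small, because virtual visits go to wounds judged unlikely to close.

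**The case against.** The strongest reply is that the size, and even the sign, depends on behaviour the documents do not fix. Virtual visits are optional, and imaging at them is not required rather than ruled out. If sites see everyone in person, the problem disappears. Investigators also have reasons to see matrix patients in person: section 5.10.3 provides for inspection, debridement and dressing changes at weekly visits, and 5.10.4 covers fenestration if exudate collects under the matrix. The SOC condition may be a small hurdle in practice, since SOC includes training on dressing changes (2.4.1) and virtual visits cover dressing advice (5.12). All of this stands, so the direction is probable rather than certain.

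A reader might infer a large, sure advantage for the matrix. With 40% judged likely to close, no unlikely matrix patient seen and half of the unlikely SOC patients seen, the means are 90 and (0.4·90 + 0.3·50)/0.7 = 72.9, a gap of 17 points. Nothing in the documents supports the assumption that no slow-healing matrix patient is seen in person. Nor do they support reading the same between-group bias into the VLU arm, or a definite bias against the matrix in detecting closure.

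It can also be said that section 9.5 requires the number of patients with each continuous summary, by group and arm, so the count imaged will be visible. That helps, but it does not tell the reader that the missing patients were those expected to heal more slowly.

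Finally, the other weeks are not free of gaps. Visits and measurement stop once all study wounds are confirmed closed, and the plan does not say whether a closed wound later counts as a 100% reduction. That is a separate question affecting every week, and it does not cure Weeks 5 and 9.

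**Conclusion.** The point holds for the DFU arm at Weeks 5 and 9. Followed as written, 9.5.5 can compare subsets selected on predicted healing under a rule that differs by group, and the plan has no method for the missing areas. Under no true difference the artefact runs from +0.3 to +14.4 points over the assumed shares of 80% against 90%, through to 20% against 90%, of unlikely patients seen in person. It is zero if the shares are equal, and it changes sign if SOC patients go virtual more often. A direction favouring the matrix is the more likely one because only SOC patients face the extra condition.

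In the VLU arm the means at these weeks may be unrepresentative. Use of virtual visits could differ by group, since the investigator who decides is not stated to be blinded, but nothing in the written rule produces a difference.

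Severity is low. The result is exploratory and untested, and two intermediate weeks are affected. A reader might infer that the primary endpoint is compromised. The documents do not support that: neither it nor the Week 12 and Week 16 areas are missing by this rule.

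**What to change.** Add one sentence to 9.5.5: in the DFU arm, between-group differences in percent area change and, for consistency, in proportion closed are not calculated at Weeks 5 and 9. Alternatively, keep those weeks as descriptive results only, labelled as a selected subset, with the number imaged and the number seen virtually in each group. The same label would suit the VLU means at those weeks.

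The cost is two exploratory timepoints in the DFU comparison. Weeks 4, 6, 8 and 10, where this exception does not apply, remain. No change to visits, treatment or sample size is needed. A longitudinal model using earlier areas, with a sensitivity analysis, would also address the gap but is more work than an untested summary needs. While 9.5.5 is open, it would be worth stating how closed wounds are counted at later weeks.
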